1.1. Study Objectives

1.1.1. Primary Objective:

- To determine whether a therapeutic approach that includes gastrectomy and/or metastasectomy plus systemic therapy is superior to the standard of care approach that includes systemic therapy alone in terms of overall survival for patients who present with limited metastatic gastric cancer (MGC).

1.1.2. Secondary Objectives:

- To compare progression-free survival (PFS) between the two study arms
- To analyze prognostic factors and generate potential selection criteria for patients who present with limited gastric cancer metastases that might benefit from gastrectomy and/or metastasectomy plus systemic therapy.
- To analyze prognostic factors and generate potential selection criteria for patients who present with limited gastric cancer metastases that will not benefit from gastrectomy and/or metastasectomy.
- To determine if surgical resection impacts the dosing and duration of subsequent chemotherapy administration
- To compare quality of life (QOL) parameters between the two study groups. We will use tools specifically developed for assessment of QOL in gastric cancer patients: FACT-Ga, EORTC QLQ-STO22 and the SROTC QLQ-C30¹⁻⁴.
- To determine and compare patterns of disease recurrence between the two therapeutic approaches and their clinical implications.

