Patient selection is critical when considering liver resection but delineating conclusive prognostic factors from several retrospective studies may be less than ideal. Analyzing the data presented in these studies may help in identifying factors that can be prospectively analyzed in a clinical trial such as this. Prognostic factors identified as being significant on univariate analysis in at least one study included the number of liver metastases (solitary vs. multiple nodules), negative resection margins, synchronous vs. metachronous presentation, certain primary tumor characteristics such as depth (serosal invasion), venous and lymphatic invasion, histologic grade, lymphocytic infiltration and fibrous pseudocapsule along with metastatic tumor characteristics such as disease free interval, size and distribution of metastases (unilobar vs. bilobar). Factors identified as significant on multivariate analysis in at least one study included the number of liver metastases (solitary vs. multiple), negative resection margins, serosal/lymphatic/venous invasion of primary tumor, and synchronous vs. metachronous presentation. Although two studies did show a significantly worse outcome for patients undergoing synchronous hepatic resections, the detailed analysis of 29 long term survivors shows that 17 patients (59%) had synchronous disease.

Considering the pattern of distant failure of gastric metastases, we believe that the majority of the study population will include patients with hepatic gastric metastases. Based on the data presented here regarding liver resection for hepatic gastric metastases and data from colorectal cancer metastatic to the liver, we propose the following selection criteria for this trial: Patients eligible for this trial may include patients with synchronous or metachronous gastric liver metastases, and liver disease (bilateral or unilateral) limited to ≤ 5 lesions and/or $\leq 15\text{cm}$.

Peritoneal Disease

The next most common mode of failure is locoregional-peritoneal disease. Sugabaker et al. categorized gastric peritoneal disease into four distinct categories defined below³⁷:

Peritoneal Staging (adapted with modifications)

P0	No peritoneal seeding
P1	Adjacent peritoneal involvement only; seeding limited to the upper abdomen only, all resectable to $\leq 0.5\text{mm}$
P2	Few scattered metastases to distant peritoneum; small-volume seeding throughout the abdomen, resectable to $\leq 0.5\text{mm}$

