2.1. Eligibility Criteria

2.1.1. Inclusion Criteria

- a. Histologically or cytologically confirmed gastric adenocarcinoma
 - b. Metastatic disease must be measurable by CT and/or MRI
 - or*
 - There must be a history of positive peritoneal washings or carcinomatosis
 - c. All disease should be deemed resectable to negative margins (NED) based on imaging studies e.g.:
 - Esophageal invasion <4cm that does not require thoracotomy (Seiwert II and III lesions)
 - Hepatic metastases (unilateral or bilateral ≤ 5 lesions, ≤ 15 cm total diameter)
 - Primary peritoneal metastases (small disease load \leq P2 disease) without massive ascites or intestinal obstruction
 - Para-aortic lymph node metastases (stations 16 a1 and/or b2, see appendix 5)
 - Lung metastases (≤ 3 unilateral/bilateral, 9 cm total diameter)
 - Patients who present with both hepatic and peritoneal metastases must have no evidence of extensive para-aortic/retro-pancreatic lymph node metastases
- Note:** Patients with both pulmonary and peritoneal metastases will be enrolled at the discretion of the PI
- d. Greater than or equal to 18 years of age
 - e. Must be able to understand and sign the Informed Consent Document
 - f. Clinical performance status of ECOG ≤ 2
 - g. Life expectancy of greater than three months
 - h. Patients of both genders must be willing to practice birth control during and for four months after receiving chemotherapy
 - i. Hematology:
 - Absolute neutrophil count greater than $1500/\text{mm}^3$ without the support of Filgrastim.
 - Platelet count greater than $75,000/\text{mm}^3$.
 - Hemoglobin greater than 8.0 g/dl.
 - j. Chemistry:
 - Serum ALT/AST less or equal to 5 times the upper limit of normal; except in the presence of obstructive liver metastases where ALT/AST may be up to 10 times the upper limit of normal
 - Serum creatinine less than or equal to 1.5 mg/dl unless the measured creatinine clearance is greater than $60 \text{ mL/min}/1.73 \text{ m}^2$
 - Total bilirubin less than or equal to 2 mg/dl, except in the presence of obstructive metastases
 - PT within 2 seconds of the upper limit of normal (INR ≤ 1.8)
 - k. No history of prior/other malignancies within the 2 years prior to enrollment with the exception of basal cell carcinoma

2.1.2.

Exclusion Criteria

- a. Prior treatment with FOLFOXIRI (treatment with any of the components as separate regimens is allowable)

- b. Inability to tolerate any of the chemotherapeutic agents

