2.3. Patient Registration, Stratification, and Randomization

Registration of patients onto this study will take place within 10 days of the patient signing the consent by faxing a completed eligibility checklist to the Central Registration Office (CRO) at [contact] between 9:00 and 5:00 Monday through Friday. Following laparoscopy, patients will be stratified and then randomized by the CRO to receive gastrectomy and/or metastasectomy plus systemic therapy (GYMS arm) or standard therapy (SA arm). The CRO will notify the Study Coordinator of the results of randomization.

Note: As soon as the patient has signed the informed consent, the patient's referring oncologist (or [name] or his designee for those patients being treated at the NCI) will be notified of the expected date of randomization and potential start dates for the chemotherapy. Immediately following randomization the referring oncologist will be notified. Subjects who are randomized to receive chemotherapy only must begin chemotherapy treatment within 14 days following randomization.

Stratification will be done according to the following factors:

- Site of metastases (liver, lung, and peritoneal disease). Note: positive peritoneal washings will be stratified as peritoneal disease.
- Time to development of first metastases (earlier than 1 year vs. later than 1 year)
- Previous systemic therapy specifically given for gastric metastases vs. no therapy for metastatic disease. (**Note:** patients who have received adjuvant chemotherapy will be stratified to the *no therapy for metastatic disease* group)

3. Study Implementation:

Study Design (See appendix 3 for trial schema)

Experimental Design:

- This is a prospective randomized trial comparing the effects of two therapeutic approaches, gastrectomy and/or metastasectomy plus systemic therapy (GYMS) to systemic therapy alone (SA) on the overall survival of patients with limited gastric cancer metastases.
- Patients who are newly diagnosed as well as those who have received prior systemic treatment for gastric metastases will be eligible. Both groups will be randomized to surgery plus chemotherapy or chemotherapy alone.
- Candidate patients for this trial will undergo all or part of the following staging elements before randomization and/or if indicated medically: pathologic confirmation of gastric cancer as feasible, H&P, laboratory evaluations, imaging studies and other studies as medically indicated.

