5.4. Statistical Section

The primary objective of the trial is to determine if there is a difference in overall survival among patients with limited gastric cancer metastases who are randomized to receive either systemic therapy alone or gastrectomy, metastasectomy and systemic therapy.

Based upon results in the literature, patients who would be eligible for this trial and who receive systemic therapy alone would be expected to have an estimated 12-month median overall survival from the date of randomization. The goal of this study will be to determine if the use of gastrectomy, metastasectomy and systemic therapy will result in an 8-month increase in overall survival, to a median of 20 months. Patients will be randomized between systemic therapy alone or gastrectomy, metastasectomy and systemic therapy and followed for overall survival. Kaplan-Meier curves and a two-tailed log-rank test will be the primary analysis methods. Assuming exponential overall survival curves, the hazard rate for the systemic therapy is 0.0578, or approximately a 5.8% probability of death each month when the median survival is 12 months. If we assume that the surgery plus systemic therapy arm has a median overall survival of 20 months, this corresponds to a hazard rate of 0.0347, and the resulting hazard ratio for the comparison of the two overall survival curves would be 1.67. To compare these curves and detect a difference with a 0.05 two-tailed log-rank test, a total of 68 evaluable subjects per arm (136 total) will need to be enrolled over a 6-year period and followed for an additional 2 years from the date of entry of the last patient, with 121 total deaths, in order to have 80% power to compare the curves.

Patients will be stratified for site of metastases (liver, peritoneal, or lung), disease-free survival and prior systemic therapy for gastric metastases.

Progression-free survival will also be evaluated using Kaplan-Meier curves, and a two-tailed log rank test, as a secondary endpoint. In addition, a prognostic factor evaluation using Cox proportional hazards modeling will take place after the study has concluded in order to identify if there are factors which can be identified that are associated with survival or progression free survival in patients randomized to treatments on this trial; this will also be interpreted as a secondary endpoint.

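### Two secondary objectives ask who benefits from surgery, but the Cox analysis described for them does not show whether surgery's relative effect differs by factor

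*Combined protocol and SAP*

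**What the plan says.** Section 1.1.2 has two linked secondary objectives, each resting on an analysis of prognosis. One is to "generate potential selection criteria for patients who present with limited gastric cancer metastases that might benefit from gastrectomy and/or metastasectomy plus systemic therapy". The other is to "generate potential selection criteria for patients who present with limited gastric cancer metastases that will not benefit from gastrectomy and/or metastasectomy". The Precis and Section 1.2 repeat the aim of characterising the patients who might benefit.

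Section 5.4 describes one analysis that matches: a Cox prognostic-factor evaluation after the study ends, as a secondary endpoint, to look for "factors which can be identified that are associated with survival or progression free survival in patients randomized to treatments on this trial". Neither Section 5.4 nor Section 5.5 gives a list of factors, a treatment-by-factor term, or a GYMS-versus-SA comparison within factor levels.

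Two other places bear on the choice of factors:

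- Section 1.2 (Hepatic Disease) says that the retrospective series may help in "identifying factors that can be prospectively analyzed in a clinical trial such as this". It lists those significant on multivariate analysis in at least one series: "number of liver metastases (solitary vs. multiple), negative resection margins, serosal/lymphatic/venous invasion of primary tumor, and synchronous vs. metachronous presentation".
- Section 2.3 stratifies randomisation by "Site of metastases (liver, lung, and peritoneal disease"), by "Time to development of first metastases (earlier than 1 year vs. later than 1 year") and by previous systemic therapy for metastases.

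**The concern.** Benefit from surgery is a contrast between arms. An association between a factor and survival is a contrast between patients who have the factor and patients who do not. A factor can be strongly prognostic while surgery changes the hazard by the same proportion with or without it. Conversely, a factor can alter the effect of surgery and show little association with survival when the arms are combined.

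If the flagged factors were read directly as selection criteria, patients could be described as good or poor candidates for a major operation on the strength of prognosis alone. Section 1.2 itself acknowledges that the surgical series are selected and retrospective. What this trial adds is the randomised SA arm, and the plan does not say that this arm will be used for the question of who benefits.

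**Working it through.** **1. Objective against method.** The objectives have two parts: prognostic factors, and selection criteria for benefit. The Cox evaluation in Section 5.4 answers the first. For the second, the text is silent: interaction terms are neither planned nor ruled out.

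**2. The plan's own figure.** Inputs from Section 5.4: medians of 12 and 20 months, two-sided alpha 0.05, power 80%, equal arms. The hazard ratio is 20/12 = 1.67 (SA to GYMS), or 0.60 as GYMS to SA. Schoenfeld's formula gives 4 × (1.960 + 0.842)² / (ln 1.667)² = 4 × 7.85 / 0.261 = 120.3, so 121 deaths. This matches the plan. D = 121 is used below.

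**3. Prognosis matters for absolute gain.** This step shows the principle only. Take one common ratio of 1.67 and a factor that doubles the hazard in both arms (assumed), with exponential survival.

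- Factor absent: median 12 to 20 months (+8); 12-month survival 50% to 66% (+16 points).
- Factor present: median 6 to 10 months (+4); 12-month survival 0.5^(12/6) = 25% to 0.5^(12/10) = 43.5% (+18.5 points).

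The absolute gain changes, and its direction depends on the measure, while the relative effect is identical. This is not the design in Section 5.4, where 12 and 20 months are whole-arm medians. With 30% of patients carrying the factor, the arm median solves 0.7x + 0.3x² = 0.5, so x = 0.573. The arm medians would then be about 9.6 and 16.0 months.

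**4. A purely prognostic factor would usually be flagged.** For a main effect, SE = 1/√(D f(1−f)), where f is the share with the factor (assumed, and treated as equal to its share of deaths). At f = 0.3, SE = 1/√25.41 = 0.198. For a factor hazard ratio of 2.0, ln 2/0.198 − 1.96 = 1.53, which is about 94% power.

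| f (assumed) | HR 1.5 | HR 1.75 | HR 2.0 |
|---|---|---|---|
| 0.2 | 43% | 69% | 86% |
| 0.3 | 53% | 81% | 94% |
| 0.5 | 61% | 87% | 97% |

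In every cell the effect of surgery is the same at both levels.

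**5. An effect modifier could be missed.** Suppose the factor's hazard ratio is 1.67 in SA and 0.60 in GYMS, with surgery having no effect when the factor is absent. The surgery hazard ratio is then 1.0 without the factor and 0.60/1.67 = 0.36 with it. The log effects of the factor, +0.51 and −0.51, roughly cancel when the arms are combined, so a main-effects model has little to detect.

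**6. What an interaction test could deliver.** With equal arms, SE of the log ratio of hazard ratios = √(4/(D f(1−f))), where f is now the share of deaths in one level. The ratio detectable with 80% power is exp(2.80 × SE).

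| Split of deaths (assumed) | SE | Detectable ratio | Power at ratio 1.67 |
|---|---|---|---|
| 50:50 | 0.364 | 2.8 | 29% |
| 30:70 | 0.397 | 3.0 | 25% |
| 20:80 | 0.455 | 3.6 | 20% |

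Within one level, SE = 2/√deaths. An observed GYMS/SA hazard ratio of 0.60 would have a 95% CI of 0.36–0.99 with 50% of deaths (60.5), 0.27–1.33 with 20% (24.2) and 0.19–1.85 with 10% (12.1). Three independent tests at 5% carry a 1 − 0.95³ = 14% chance of at least one false positive.

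**The case against.** The best defence is that the plan does what it says. The objectives name prognostic factors, and a prognostic Cox model is planned. They speak of potential criteria, so the aim is hypothesis-generating. The model terms are left open, and interactions could be fitted. Prognosis is also relevant to selection, as step 3 shows. All of this stands. It limits the point to what is not described, and to a secondary analysis.

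It can also be said that 121 deaths are too few for interaction tests. That is right as a limit on what can be learned. It argues for few factors, intervals and an exploratory label. It does not make a well-powered prognostic test an answer to a different question.

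A reader might infer from Section 1.2 that a list of factors was promised and then dropped from Section 5.4. The text does not support this. It says only that the retrospective data may help identify factors, and it goes on to use them to propose eligibility limits. Nor does the plan propose to compare the arms by resection margin. Margins matter here only as a factor to keep out of any such comparison, because they are known only after surgery.

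**Conclusion.** The point holds as a mismatch between objective and described method. Followed as written, the Cox evaluation can flag purely prognostic factors and can miss factors that modify the effect of surgery. The consequence is confined to an exploratory secondary analysis, and the remedy is a cheap improvement.

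Three stronger conclusions are not supported:

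- That the primary result is at risk. The two-sided log-rank comparison of overall survival does not depend on this analysis.
- That the Cox results would be useless for selection. They bear on absolute gain.
- That the 94% figure measures a defect in this trial. It rests on an assumed factor hazard ratio and prevalence. The documents give neither prevalences nor the split of deaths by factor, so all the power figures here are illustrations over stated ranges.

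**What to change.** In Section 5.4, for overall survival, add exploratory Cox models containing treatment, factor and their interaction, for three prespecified factors:

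1. Time to first metastasis, before versus after 1 year.
2. Prior systemic therapy for metastases, yes versus no.
3. Site, as one binary contrast: any peritoneal disease, including positive washings, versus none, as known at randomisation.

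The binary site contrast is needed because the three levels in Section 2.3 do not place every patient. Section 2.1.1 admits "Patients who present with both hepatic and peritoneal metastases", and Section 2.3 gives no rule for patients with several sites. Patients whose only metastases are para-aortic nodes (Sections 2.1.1 and 3.2.7) fit none of the levels. Under the contrast every patient, including those with lung disease, has exactly one level. Lung cases are otherwise only described, since Section 1.2 expects them to be rare.

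Do not use factors known only after surgery as effect modifiers. Report the GYMS/SA hazard ratio with 95% CI in each level, the interaction estimate, and the number of interactions examined, as Section 5.4 already does for the quality-of-life tests. Label the analysis exploratory. State that main effects are prognostic and are not by themselves evidence that the effect of surgery differs.

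The cost is three model fits and a few sentences. The first two factors are recorded for randomisation, and the third follows from the staging done before it. No extra patients or visits are needed, and the primary test does not change. The drawback is the low precision shown in the working: the analysis corrects what is estimated and how it is labelled, but is unlikely to settle who benefits.

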The study will be monitored by the NCI/CCR Data Safety and Monitoring Board on an annual basis to evaluate the safety of the two arms. The SAEs (typically grade 3 toxicities, or greater) will be reported according to type of toxicity, and maximal grade noted per patient, for toxicities with at least a possible attribution to the therapy provided on that arm. Comparisons will be made between the two arms using Cochran-Armitage tests for trend, or other appropriate methods, to determine if there is increased toxicity associated with either arm.

In addition, at the first Data Safety and Monitoring Board (DSMB) meeting held following the point at which half of the required total subjects have been enrolled (68 total), a single evaluation for futility will be undertaken. Evaluations for better than expected efficacy will also be made annually, beginning after half the subjects have been enrolled.

The futility evaluation will be performed as follows: based on the full data available at the time, a conditional power analysis will be performed to determine if the trial is unlikely to find an effect at the 0.05 two-tailed significance level with continued accrual based on an overall survival endpoint. Median survivals of 12 and 20 months correspond to 12-month survivals of 50% and 66% respectively. Using these as the values under the alternative, and using the actual proportions alive at 12 months, based on the observed fractions and the expected sample sizes at 12 months, the conditional power of the trial will be determined assuming accrual of the remaining patients to achieve a total of 136 patients. If the conditional probability of finding a difference at the two-sided 0.05 level at the conclusion of the trial is less than 20%, then it will be reasonable to recommend that no further patients will be enrolled.

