5.5. Safety and Monitoring Plan

Careful evaluation to ascertain the toxicity and clinical response will be performed. The principal investigator will monitor the data and toxicities to identify trends quarterly. The principal investigator will be responsible for revising the protocol as needed to maintain safety. The NCI IRB will review submitted adverse events

monthly to also evaluate trends and will require a follow up plan from the principal investigator whenever a trend is identified.

The trial will be monitored at least annually by the NCI/CCR DSMB. Interim outcome results will not be revealed to the investigators of the trial; results will be presented to the investigators prior to final accrual to the trial only if the DSMB recommends early termination of the trial. Until 68 patients have been randomized, only toxicity and adverse events will be examined at each review. Once 68 patients have been randomized, interim evaluations to determine whether there is sufficient evidence to terminate accrual because of a better than expected improvement in overall survival, will be performed as detailed in Section 5.4. At the first such review of outcomes, a single evaluation for futility will also be performed.

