7.1.4. Serious

An adverse event or suspected adverse reaction is considered serious if in the view of the investigator or the sponsor, it results in any of the following:

- Death,

- A life-threatening adverse drug experience
- Inpatient hospitalization or prolongation of existing hospitalization
- Persistent or significant incapacity or substantial disruption of the ability to conduct normal life functions
- A congenital anomaly/birth defect.
- Important medical events that may not result in death, be life-threatening, or require hospitalization may be considered a serious adverse drug experience when, based upon appropriate medical judgment, they may jeopardize the patient or subject and may require medical or surgical intervention to prevent one of the outcomes listed in this definition.

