7.4.2. NCI-IRB Requirements for PI Reporting of Adverse Events at Continuing Review

The protocol PI will report to the NCI-IRB:

- All Grade 2 unexpected events that are possibly, probably or definitely related to the research;
- All Grade 3 and 4 events that are possibly, probably or definitely related to the research;
- All Grade 5 events regardless of attribution;
- All Serious Events regardless of attribution.

NOTE: Grade 1 events are not required to be reported

8. Pharmaceutical Information:

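### The only specified between-arm safety comparison counts events attributed to each arm's own therapy, so it can hide or inflate a true difference in harm, and no all-cause comparison by arm is planned

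*Combined protocol and SAP*

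**What the plan says.** Section 5.4 assigns the annual safety review of the two arms to the DSMB. "The SAEs (typically grade 3 toxicities, or greater) will be reported according to type of toxicity, and maximal grade noted per patient", and the report is limited to events "for toxicities with at least a possible attribution to the therapy provided on that arm". The next sentence builds the comparison on that report: "Comparisons will be made between the two arms using Cochran-Armitage tests for trend, or other appropriate methods", the aim being "to determine if there is increased toxicity associated with either arm". No significance level, power or action threshold is given.

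Other sections treat attribution differently:

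- **7.1.1** defines an adverse event without regard to relatedness.
- **7.4.2** sends the IRB, at continuing review, "All Grade 5 events regardless of attribution", and likewise every serious event.
- **5.5** states: "Until 68 patients have been randomized, only toxicity and adverse events will be examined at each review". It neither repeats the attribution filter nor specifies an all-cause analysis.

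The only blinding described is that of the radiologist who measures progression (Section 3, Experimental Design). The documents do not say who assigns attribution.

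**The concern.** Randomisation makes all-cause event rates comparable between arms. Restricting the count to events thought related to treatment gives up part of that protection, because a judgement made with knowledge of the arm now decides what is counted.

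The problem is sharper than usual here because the reference for the judgement changes with the arm. In GYMS the therapy is major surgery, heated peritoneal perfusion for intra-abdominal disease, and chemotherapy. In SA it is chemotherapy. The same clinical deterioration is tested against two different causal questions. It might be ascribed to disease in one arm and to treatment in the other, or the wider range of GYMS treatment might draw in events that would be called unrelated in SA.

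What is at stake is the comparison the DSMB relies on to judge whether either arm is more toxic. It matters most early, because until 68 patients are randomised the DSMB does not review survival, which would count every death without any attribution step.

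**Working it through.** **Is an all-cause comparison planned elsewhere?** Setting 5.4, 5.5, 7.1.1, 7.2, 7.3 and 7.4 side by side, the answer is no. All-attribution information exists as definitions, data capture and IRB listings. The only analysis that compares toxicity between arms is the one in 5.4, and it is filtered.

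**How long is the period without survival review?** Section 5.4 expects 24 patients a year, so 68 / 24 = 2.8 years, with about 68 / 2 = 34 patients per arm at its end.

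**How far could the filter move the comparison?** The plan gives no figure for toxicity, so there is none to reproduce. The rates below are assumptions. Let pG and pS be the true proportions of patients with a grade 3+ event, and aG and aS the proportions of those patients whose event passes the filter. Then

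tabulated excess = pG × aG − pS × aS.

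Power uses the two-proportion normal approximation at two-sided 0.05 (my threshold, as a stand-in for the trend test) with n per arm:

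Φ{(d − 1.96 × √[2p̄(1 − p̄)/n]) / √[(p1(1 − p1) + p2(1 − p2))/n]}.

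For 0.60 vs 0.40 with n = 68: (0.200 − 1.96 × 0.0857) / 0.0840 = 0.38, and Φ(0.38) = 0.65.

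| True GYMS / SA | Attribution GYMS / SA | Tabulated GYMS / SA | Excess (points) | Power, 68 per arm |
|---|---|---|---|---|
| 60% / 40% | no filter | 60% / 40% | 20 | 65% |
| 60% / 40% | 90% / 90% | 54% / 36% | 18 | 56% |
| 60% / 40% | 70% / 90% | 42% / 36% | 6 | 11% |
| 60% / 40% | 90% / 70% | 54% / 28% | 26 | 88% |

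At 34 per arm, the first row gives 38% and the third 7% (8% if both tails are counted).

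Three things follow:

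- Equal filtering costs little. At 90% in both arms the excess shrinks from 20 to 18 points. Unequal filtering does the damage.
- The direction depends wholly on which arm has the higher attribution rate. With SA at 90%, the excess is 0 when GYMS attribution is 60% (36% vs 36%) and 12 points when it is 80% (48% vs 36%). With the rates reversed it is inflated.
- The result does not depend on one set of true rates. With 50% vs 30% and all SA events counted, dropping 25% of affected GYMS patients gives 37.5% vs 30%: the excess falls from 20 to 7.5 points and power at 68 per arm from 67% to 15%.

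**Sensitivity to the per-patient summary.** Section 5.4 uses the maximal grade per patient, and a patient with several qualifying events is counted if any one is attributed. Suppose each affected patient has two independently attributed events. At 70% / 90% attribution, retention is 1 − 0.3² = 91% and 1 − 0.1² = 99%. The tabulated rates become 0.60 × 0.91 = 54.6% and 0.40 × 0.99 = 39.6%, an excess of 15 points instead of 6.

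**The case against.** The strongest reply is that the filter is loose and the data are not lost. An event needs only a possible link to therapy, so most post-operative events should pass. The IRB receives all serious and all grade 5 events at continuing review, gets expedited reports of deaths other than from progression (7.4.1), and looks for trends monthly (5.5). Section 5.5 lets the DSMB examine adverse events, which 7.1.1 defines without regard to cause. All of this stands and limits the severity. It does not supply a planned comparison by arm free of attribution: IRB listings are not that, and 5.5 describes access, not an analysis.

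Several stronger readings are tempting but not supported:

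- **That the filter hides GYMS harm.** GYMS treatment is broader, so more events may be attributable there. The documents give no attribution rates.
- **That different people judge the two arms.** Surgery is done only at the NCI (3.1.2), but 3.5.1 allows local oncologists to give systemic therapy without limiting this to SA, and 7.2.1 routes all events through one designated research nurse.
- **That a GYMS death ascribed to disease is invisible to the DSMB before 68 patients.** It may fall outside the 5.4 comparison, but 5.5 does not bar the DSMB from seeing it.
- **That a grade 2 event leading to hospitalisation is left out.** Section 7.1.4 counts "Inpatient hospitalization or prolongation of existing hospitalization" as serious. The mention of grade 3 in 5.4 is a loose gloss on serious events and does not clearly exclude such a case.
- **That an unfiltered database is already there to tabulate.** Section 7.2.1 narrows capture more than 30 days after last treatment to events that are serious, unexpected and related. Section 7.3 also keeps some grade 3 and 4 events out of C3D. An all-cause table must state these limits.

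**Conclusion.** The concern holds. The one between-arm safety comparison the plan specifies depends on a relatedness judgement that is defined differently for each arm and made with knowledge of the assignment. No all-cause comparison is planned to set beside it. A true difference in harm can be hidden or inflated.

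The size cannot be established from the documents. Under assumed true rates of 60% and 40%, a 20-point difference in attribution moves the tabulated excess to 6 or 26 points, depending on its direction; if patients have several events each, the distortion is smaller. These figures show that the comparison is sensitive to attribution. They do not estimate what will happen in this trial.

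The change should be made because it is inexpensive and removes a source of bias in either direction. The primary survival analysis, the sample size and treatment are unaffected.

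**What to change.** **In 5.4:** make the main by-arm DSMB safety comparison, counted from randomisation and regardless of attribution, consist of

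- all captured grade 3+ events,
- all events serious under 7.1.4, and
- all grade 5 events.

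Keep the table of at least possibly related events as a secondary display.

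**State the coverage.** The grade 3+ table covers events captured in C3D under 7.2 and 7.3. Not captured are grade 3 and 4 events that resolve within 72 hours of surgery (7.3.2), package-insert grade 3 events during chemotherapy that need no hospital admission (7.3.4) and, more than 30 days after last treatment, events that are not serious, unexpected and related (7.2.1). Take deaths and serious events from the all-attribution listing already prepared for the IRB under 7.4.2.

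**In 5.5:** add a sentence that deaths by arm are shown to the DSMB as safety data before 68 patients are randomised and are not a formal efficacy look. Without it, the new table would appear to conflict with the rule that withholds outcomes until then.

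**Cost:** one more table in each annual report, the matching sentence in 5.5, and some dilution of treatment effects by disease-related events, which the secondary table helps to interpret. No change to data capture is needed if the coverage limits are stated.
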